Does an information leaflet provide an effective way of communication in the peri-procedure period? Will it help in better information delivery and hence reduce the number of avoidable postponements and delay. And does this translate to better patient satisfaction is what this study aims to see. The study is restricted to patients undergoing Head & Neck procedures under General Anaesthesia, as they form the major bulk of patients in our minor OT complex and for logistic reasons to start with a defined group of patients.

AIMS AND OBJECTIVES:

1. To reduce postponement of cases due to lack of information to patients in the pre-operative period
2. To compare satisfaction levels between patients , pre and post introduction of information leaflet

Primary end point:

To reduce postponement of cases due to lack of information to patients in the pre-operative period

Co Primary end point:

To compare satisfaction levels between patients, pre and post introduction of information leaflet.

Design of the study: Pre and post interventional model

INCLUSION CRITERIA:

All adult patients (> 18yrs), ASA I-III, undergoing elective therapeutic/diagnostic Head & Neck surgeries under General Anaesthesia in the Minor OT complex and discharged on the same day will be included. The surgeries will include Head & Neck surgeries like DL scopes, laser surgeries, EUA, excision biopsies etc.

EXCLUSION CRITERIA:

1. Patients refusing to take part in study
2. Patients undergoing emergency surgeries
3. ASA IV patients, or high risk patients planned for admission
4. Admitted patients for minor OT procedure
5. Patients not getting the Information leaflet due to any reason (in 2nd half of study)
6. Patient and his attendant, both illiterate

MATERIAL AND METHODS

After Institutional Review Board approval, all adult patients meeting inclusion criteria and undergoing surgeries in the Minor OT complex during a 6 month period will be enrolled in the study. The study will be done in two parts.

In the First half of study- planned over 2 months (Nov-Dec), feedback forms will be collected from patients at the end of minor OT procedure (Annexure 2.1) All patients, meeting inclusion criteria, at the end of the procedure prior to discharge from the minor OT will be explained about the study and they shall be given a feedback form to be filled and submitted. Also the number of postponement or rescheduling of cases will be noted.

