Postponement or rescheduling of case is defined as an event when the patient who is called for his turn in minor OT is deferred for any amount of time in account of starvation not adequate, investigations not brought, medications not taken as prescribed. Any postponement in view of awaiting opinion from senior consultant , special equipment or any investigations called in view of patients clinical conditions which was not anticipated in the OPD by the surgical colleague, or due to lack of OT time will not be included.

After the initial collection of feedback over 2 months, the patient information leaflet (PIL) will be handed over to all patients planned for procedure in the minor OT complex (Second half of study). This leaflet will be handed over by the attending doctor in the Head neck OPD. The checklist pertaining to counselling at the Head neck OPD will be ticked after they are carried out. The patient will be instructed to read leaflet carefully and carry the leaflet on the day of Minor OT procedure. In the minor OT the discharge checklist in the PIL would be carried out by all concerned including the surgical, anesthesia and nursing team. A period of 1 month (Jan) will be allowed to streamline the use of patient information leaflet.

In the subsequent 2 months, Feb - Mar, the impact of use of PIL will be assessed. Firstly by noting the number of postponement or rescheduling of cases. In addition all patients meeting inclusion criteria will be given the feedback form (Annexure 2.2) at the end of their procedure in minor OT.

For patients coming to minor OT without a patient information leaflet- one would ascertain if the leaflet was handed in OPD and not brought to minor OT or if the leaflet was not handed at all. The numbers of such misses will be recorded. Patients who did not get the leaflet in the OPD will be excluded from study.

Sample size calculation:

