For our preliminary review of postponement rate as defined in our study is around 20%. We aim for a reduction of such postponement by 50%. Group sample sizes of 199 in group 1 and 199 in group 2 achieve 80.007% power to detect a difference between the group proportions of -0.1000. The proportion in group 1 (the treatment group) is assumed to be 0.2000 under the null hypothesis and 0.1000 under the alternative hypothesis. The proportion in group 2 (the control group) is 0.2000. The test statistic used is the two-sided Z-Test with pooled variance. The significance level of the test is 0.0500. Considering a 20% loss to follow up from OPD to minor OT, the sample size needed is 480 patients. On an average at least 250 patients of head neck patients undergo procedure under general anesthesia, per month (12-15 patients /day x 20 working days). With due consideration of our inclusion criteria, a two month recruitment period pre and post intervention should be adequate.

MEASUREMENTS

- No. of cases postponed pre and post introduction of the leaflet and reasons behind them
- Primary data collected will be patient satisfaction levels after the procedure (both pre and post PIL) on a 5 point Likert scale (Ranging from very poor = 0 to Excellent = 4)
- No of patients who did not receive the patient information leaflet in the OPD
- No of patients who received the PIL but did not get it along to the minor OT

STATISTICAL ANALYSIS

All Data will be analyzed using SPSS software. Likert scores will be treated as ordinal data. Proportions will be compared using chi square analysis. Additionally Multivariate logistic regression analysis will be used to assess the contribution of possible covariates, including age sex and patient knowledge on patient satisfaction. For all data P-value < 0.05 will be considered as statistical significant.

REFERENCES:

1. Beverly K. Philip MD, Day Care Surgery: The United States Model of Health Care IAAS Journal/17.4/PHILIP17.4.pdf
2. Emerging Trends in Healthcare A Journey from Bench to Bedside 17 February 2011;KPMG/ASSOCHAM
3. Jarrett, P. E. M, Day care surgery ;European Journal Of Anaesthesiology November 2001 - Volume 18 - Issue - p 32–35

Annexure 2.1

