5. Were you adequately informed with regard to the fasting procedure, pre-surgery (What to eat/drink)?

Yes No Not sure

6. Were you informed about any tests (blood tests, ecg, scans,x-ray etc.) that were necessary before the procedure?

Yes No Not sure

7. If you take any medicine on a regular basis, were you informed about which medicines to continue or to avoid on the day of surgery?

Yes No Not sure

8. Did you receive enough information about the future course of action about your treatment (includes when to expect the result of today's procedure, future treatment & follow up)

Yes No Not sure

9. Have you received any Information leaflet at the OPD?

Yes No

If "yes "have you read the leaflet?

Yes No

If "yes "have you understood the information provided in the leaflet?

Yes No

10. What is your opinion about the leaflet?

Very Good Good Average Bad Very Bad

11. Would you recommend this leaflet to others?

Strongly recommend / will Recommend/ Neutral /recommend reluctantly/ not recommend at all

12. How was your overall satisfaction with respect to the information you were provided before the surgery?

Excellent Very good Good Poor Very Poor

13. How was your overall satisfaction with respect to the information you were provided after the surgery?

Excellent Very good Good Poor Very Poor

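### In Feb-Mar, leaflet receipt for patients arriving without it is ascertained at the minor OT with no named handover record, so a misclassified patient and any postponement leave the post period only

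*Combined protocol and SAP*

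**What the plan says.** The relevant text is in MATERIAL AND METHODS, in the description of the second half of the study. The attending doctor in the Head & Neck OPD hands over the leaflet and the patient is told to bring it on the day. For patients who come to the minor OT without one, "one would ascertain if the leaflet was handed in OPD and not brought to minor OT or if the leaflet was not handed at all". Two consequences follow: "The numbers of such misses will be recorded", and "Patients who did not get the leaflet in the OPD will be excluded from study". Exclusion criterion 5 repeats the exclusion and limits it to the second half.

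The nearest thing to an OPD record is a counselling checklist: "The checklist pertaining to counselling at the Head neck OPD will be ticked after they are carried out". The discharge checklist is stated to be in the leaflet; the location of the OPD checklist is not stated.

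MEASUREMENTS lists two counts that depend on the same classification: "No of patients who did not receive the patient information leaflet in the OPD" and "No of patients who received the PIL but did not get it along to the minor OT". Annexure 2.2, item 9, completed after the procedure by the patient or a proxy, asks "Have you received any Information leaflet at the OPD".

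The primary event is defined in the same section as a deferral, when the patient is called for his turn in the minor OT, because of inadequate starvation, missing investigations or medications not taken as prescribed.

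**The concern.** The issue is how receipt is measured. Whether true non-recipients should be excluded at all is a separate question.

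Receipt decides who is in the Feb-Mar denominator. For the patients in doubt it is ascertained in the place where the primary event is declared, and nothing fixes it beforehand. The plan does not say what record is consulted, who decides, whether this happens before or after a deferral, or what to do when the answer is unclear. The OPD checklist is ticked, but it is not said to record handover, to be kept apart from the leaflet, or to decide the exclusion.

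Forgetting the leaflet and arriving unprepared may well go together; the background itself groups missed instructions with failure to carry essential documents. If such a patient received the leaflet but is recorded as not handed, the patient and the postponement both disappear from Feb-Mar. Nov-Dec has no matching filter, so the error does not cancel between periods. At stake is a spurious or inflated fall in the primary rate.

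The same error moves patients between the two leaflet counts. Those counts are not linked to outcome, so they would not show whether the excluded patients had been postponed.

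**Working it through.** **Step 1: reproduce the plan's figure.** Inputs from the sample size section: 0.20 v 0.10, 199 per group, two-sided pooled Z-test at 0.05.

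- SE under the null = √(2 × 0.15 × 0.85 / 199) = 0.03580
- SE under the alternative = √((0.16 + 0.09) / 199) = 0.03544
- Power = Φ((0.10 − 1.96 × 0.03580) / 0.03544) = Φ(0.842) = 0.8001

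This matches the stated 80.007%.

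**Step 2: the rate after misclassification.** Assume no leaflet effect, so the true rate is 20% in both periods. The next four inputs are assumptions, because the documents give none:

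- w, share of recipients arriving without the leaflet: 5-20%
- r, postponement risk among them: 40%
- m, share of the postponed among them wrongly recorded as not handed: 25-50%
- k, the same share among those not postponed: 10%

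Postponed patients wrongly removed: a = w·r·m. Others wrongly removed: b = w·(1 − r)·k. Observed Feb-Mar rate: p′ = (0.20 − a) / (1 − a − b).

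Mildest case: a = 0.05 × 0.4 × 0.25 = 0.005, b = 0.05 × 0.6 × 0.1 = 0.003, p′ = 0.195 / 0.992 = 0.197.

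Worst case: a = 0.2 × 0.4 × 0.5 = 0.04, b = 0.2 × 0.6 × 0.1 = 0.012, p′ = 0.16 / 0.948 = 0.169.

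**Step 3: the chance of a false significant reduction.** With the Step 1 test, this is Φ((0.20 − p′ − 1.96·SE0) / SE1), where SE0 = √(2·p̄(1 − p̄)/n), p̄ is the mean of 0.20 and p′, and SE1 = √((0.16 + p′(1 − p′))/n). In the worst case at n = 199, SE0 = 0.0389 and SE1 = 0.0389, giving Φ((0.0312 − 0.0762) / 0.0389) = Φ(−1.16) = 0.12.

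| w | m | Wrongly removed (a + b) | Feb-Mar rate | False reduction, 199 per group | 240 per group |
|---|---|---|---|---|---|
| 5% | 25% | 0.8% | 19.7% | 3.0% | 3.1% |
| 10% | 25% | 1.6% | 19.3% | 3.7% | 3.8% |
| 20% | 25% | 3.2% | 18.6% | 5.4% | 5.8% |
| 10% | 50% | 2.6% | 18.5% | 5.8% | 6.2% |
| 20% | 50% | 5.2% | 16.9% | 12% | 14% |

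The nominal value is 2.5%. The 240 column is the plan's total of 480 divided by two. The table takes equal numbers analysed; shrinking the post group for the removals changes an entry by about 0.3 of a percentage point at most.

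**Step 4: cross-check with fewer inputs.** Let f be the share wrongly excluded and q their postponement rate, so the observed rate is (0.20 − f·q)/(1 − f). With 199 per group before exclusion:

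- f = 2% and q = 40/60/80%: rate 19.6/19.2/18.8%, two-sided type I error 5.1/5.5/6.1%.
- f = 5% and the same q: rate 18.9/17.9/16.8%, two-sided type I error 5.8/8.2/12.6%.
- q = 20%: no bias at any f.

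Both routes agree: negligible when about 2% are wrongly excluded, and material from about 5% if most of those were postponed.

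**The case against.** The plan says only that staff would ascertain handover. A reader might infer that receipt is settled by asking the patient, after the deferral, and that patients or staff then have a motive to answer not given. The documents support none of these. No method is stated, so staff could check with the OPD or consult its checklist. The wording ties the check to arrival without a leaflet, whereas the event occurs when the patient is called; if status were fixed on arrival, knowledge of the event could not drive it. Nothing is said about motives. Nor do the documents show that the OPD checklist travels with the leaflet: only the discharge checklist is placed there, and the leaflet itself is not in the text.

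On size, every misclassification input is assumed. The 12% needs one recipient in five to arrive without the leaflet, twice the average postponement risk, and a fivefold difference in misrecording (50% v 10%). A reader might also run the worst case at 480 per period (12 patients × 20 days × 2 months), which gives about 23%. That throughput is before the inclusion criteria are applied, and the plan's 480 is a total for both periods.

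Some protection exists: both kinds of miss are counted, reasons for postponement are noted, and item 9 gives a second answer on receipt. A very large not-received count would be visible. Item 9 does not decide exclusion, so disagreement with it is not in itself a defect.

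What remains is that no handover record is designated, no timing or default is set, the exclusion acts in one period only, and the counts do not reveal postponements among the excluded. Early ascertainment would remove the influence of the outcome, but the plan does not require it.

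**Conclusion.** The point holds as a weakness in how receipt is established, and it should be corrected. The plan allows an outcome-related error in one period only; it does not show that one would occur, or how often.

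Under the stated assumptions a true 20% reads as 19.7% to 16.9% in Feb-Mar. The chance of a false significant reduction is 3.0% to 12% at 199 per group, and up to about 14% at 240 per group, against 2.5%. Most combinations examined lie at the lower end. The direction favours the leaflet whenever the wrongly excluded patients are postponed more often than the rest. There is no bias if the error is unrelated to outcome and these patients carry average risk.

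This is more than a missing detail, because a record made at handover cannot be created afterwards.

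**What to change.** At handover, the attending doctor in the Head & Neck OPD marks leaflet given (yes/no, with date) in the case file or the minor OT booking entry, kept apart from the leaflet. Alternatively, name a retained copy of the OPD checklist for this purpose and add a handover line to it.

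Reword the rule in MATERIAL AND METHODS along these lines: receipt is classified only from the OPD handover entry, without regard to postponement; a patient marked as given, or whose entry is blank or unclear, remains in the study. Take both leaflet counts in MEASUREMENTS from that entry, use Annexure 2.2 item 9 only as a descriptive check, and report the number of postponements among patients excluded as not given.

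The cost is one extra tick per patient and a reworded sentence. Some true non-recipients will be kept in, which slightly dilutes any effect. The design figures of 199 per group and 80% power are unchanged. The entry must be in use for every patient whose procedure falls in Feb-Mar; the January run-in month is a natural time to introduce it.

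### The inflated total of 480 does not follow from 199 per group and a 20% loss: 398/0.8 gives 498, and 480 covers a loss of only about 17% (minor)

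*Combined protocol and SAP*

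**What the plan says.** The only statement of the study's size is in the Sample size calculation paragraph of the combined protocol and SAP. It assumes a postponement rate of 20% without the leaflet and a halving to 10% with it, tested with a two-sided pooled-variance Z-test at the 5% level. On that basis, "Group sample sizes of 199 in group 1 and 199 in group 2 achieve 80.007% power".

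It then adds an allowance for attrition: "Considering a 20% loss to follow up from OPD to minor OT, the sample size needed is 480 patients". No inflation formula is given. The paragraph does not say whether the 480 are counted when surgery is planned in the OPD or on arrival at the minor OT. Nor does it say whether the 20% applies to both periods or to one.

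The paragraph goes on to expect at least 250 head and neck procedures under general anaesthesia per month. After a general reference to the inclusion criteria, it concludes that "a two month recruitment period pre and post intervention should be adequate".

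The Material and Methods section describes how patients enter. It says that "all adult patients meeting inclusion criteria and undergoing surgeries in the Minor OT complex during a 6 month period will be enrolled". In the first period, eligible patients "at the end of the procedure prior to discharge from the minor OT will be explained about the study". In the leaflet period, "all patients meeting inclusion criteria will be given the feedback form (Annexure 2.2) at the end of their procedure in minor OT".

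**The concern.** Three figures are stated together: 398 evaluable patients, a 20% loss and a total of 480. If the loss applies to both periods, they cannot all be true, because 480 less 20% is below 398. A reader who wants to check the planned size, or later to judge whether the target was met, has only this paragraph to work from, and its last figure does not follow from its inputs.

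What could be at stake is power. If 480 were treated as a recruitment target in the OPD and 20% were then lost, the comparison of postponement rates would fall slightly below the 80% planned. The unstated counting stage and period add to the problem, since the right inflated total depends on both.

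**Working it through.** **Inputs, all from the Sample size calculation paragraph**

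- Control rate: "The proportion in group 2 (the control group) is 0.2000".
- Leaflet rate: "is assumed to be 0.2000 under the null hypothesis and 0.1000 under the alternative hypothesis", so 0.10 is the value used for power.
- Two-sided Z-test with pooled variance, alpha 0.05, so the critical value is 1.960.
- 199 per group, 398 in total; loss 20%; stated total 480.

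**Step 1. Reproduce the plan's base figure**

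Power = Φ[(|p₁ − p₂| − 1.960 × SE₀) / SE₁], where

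- SE₀ = √[p̄(1 − p̄)(1/n₁ + 1/n₂)], with p̄ the pooled proportion
- SE₁ = √[p₁(1 − p₁)/n₁ + p₂(1 − p₂)/n₂]

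With 199 per group:

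- p̄ = 0.15
- SE₀ = √(0.15 × 0.85 × 2/199) = 0.03580
- SE₁ = √(0.09/199 + 0.16/199) = 0.03544
- (0.10 − 1.960 × 0.03580)/0.03544 = 0.842, and Φ(0.842) = 0.80007

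This matches the plan's 80.007%. With 198 per group, power is 79.8%, so 199 is the smallest adequate size. The base is correct.

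**Step 2. Apply the 20% loss**

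If a fraction d of those who start is lost, the number to start with is N/(1 − d).

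- 398/(1 − 0.20) = 497.5, rounded up to 498
- Per group: 199/0.80 = 248.75, rounded up to 249; 2 × 249 = 498
- Check: 249 × 0.80 = 199.2, which keeps 199

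The plan's 480 does not match. The gap is 498 − 480 = 18 patients, or 18/498 = 3.6%.

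**Step 3. What 480 does cover**

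- After a 20% loss: 480 × 0.80 = 384, or 192 per group, which is 398 − 384 = 14 short
- Largest loss that still leaves 398: 1 − 398/480 = 0.171, or 17.1%

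**Step 4. Where 480 may have come from (inference; no formula is given)**

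- 398 × 1.2 = 477.6
- 400 × 1.2 = 480 exactly, as if 199 had been rounded to 200 per group and 20% then added

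Either route adds 20% to the evaluable number. That does not offset the loss of 20% of the larger starting number.

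**Step 5. Power under each reading of 480, assuming an equal split of 240 and 240**

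| Reading of 480 | Evaluable, control vs leaflet | Power |
|---|---|---|
| Counted in the OPD, 20% lost in both periods | 192 vs 192 | 78.6% |
| 20% lost in the leaflet period only | 240 vs 192 | 82.3% |
| Counted at the minor OT, after any loss | 240 vs 240 | 86.8% |

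The formula is that of Step 1. For 240 vs 192, the pooled proportion is (240 × 0.20 + 192 × 0.10)/432 = 0.1556.

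**Step 6. Total required under each reading**

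- Loss in both periods: 249 + 249 = 498
- Loss in the leaflet period only: 199 + 249 = 448
- Counted at the minor OT, no inflation: 199 + 199 = 398

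None of these is 480.

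**The case against.** The strongest reply is that 480 comes from a choice of convention and not from a slip. Rounding 199 to 200 per group and adding 20% gives exactly 480, and the plan does not claim to have divided by 0.8. That probably explains the number, but it does not make it correct for the purpose stated. The plan describes the 20% as a loss between OPD and minor OT, which is a fraction of those who start.

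The second reply is that the shortfall is hypothetical, and most of this stands. Only one of the three readings falls below 80%, and it fits the design poorly. In both periods patients are given the form at the end of their procedure, after any loss between OPD and OT has happened. All eligible patients in each window are to be taken, and nothing stops recruitment at 480. At 250 procedures a month, a two-month window sees about 500 before the inclusion criteria are applied. The eligible share is not given; if it were half (an assumption), each period would yield 250, above both 199 and 249. No shortage of power has therefore been shown.

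The third reply is that replacing 480 by 498 presumes OPD-stage counting and loss in both periods. This is fair. If only the leaflet period is affected, 448 suffices; if patients are counted at the OT, 398 does. The stage and period should be settled first. The reply does not rescue 480, which follows from none of these readings.

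**Conclusion.** The concern holds, as a minor point. The stated total does not follow from the plan's own inputs: with 20% lost in both periods the figure is 498, not 480, a difference of 18 patients (3.6% of 498). A total of 480 allows for a loss of about 17%.

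The division is certain. The effect on power is conditional. It would be a drop from 80.0% to 78.6%, and only if 480 is an OPD-stage total, split equally, reduced by 20% in both periods, with enrolment ending there. Since the plan recruits through fixed windows at the OT, the finding is that the paragraph is internally inconsistent and leaves the basis of its target unstated. It is not a finding that the study is too small.

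**What to change.** In the Sample size calculation paragraph:

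1. State whether the inflated total is counted in the OPD or at the minor OT, and whether the 20% loss applies to both periods or only to the leaflet period.
2. If it is an OPD-stage total with loss in both periods, give 498 (249 per period) and show 398/0.8.
3. Alternatively, keep 480 and state that it allows for about 17% loss, or that it gives about 78.6% power after a 20% loss from both periods.
4. If loss is confined to the leaflet period, the derived total is 448. If patients are counted at the OT, it is 398. In either case 480 may stand as a target above the minimum, provided it is described as such.

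The cost is a one-line text correction. The design, the two-month windows and the analysis are unchanged, and the correction calls for no enrolment beyond what those windows already take in.

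### The chi-square for postponement treats patients on the same operating day as independent; if same-day postponements are positively correlated, its P-value is too small

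*Combined protocol and SAP*

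**What the plan says.** The study is a pre/post comparison: November-December without the leaflet, January to settle its use, February-March with it (MATERIAL AND METHODS). All eligible patients in each period are enrolled.

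For the analysis, STATISTICAL ANALYSIS states "Proportions will be compared using chi square analysis", with P < 0.05 as the criterion. This is the only sentence that covers postponement, the primary end point. The sample size calculation uses the matching test: "The test statistic used is the two-sided Z-Test with pooled variance", and "Group sample sizes of 199 in group 1 and 199 in group 2 achieve 80.007% power" for 20% against 10%. The same paragraph gives throughput as "12-15 patients /day x 20 working days", then says that the inclusion criteria have been considered. It does not give the number of eligible patients per day.

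A postponement is counted when a patient called to the minor OT "is deferred for any amount of time in account of starvation not adequate", or because investigations were not brought or medications not taken. Delays for lack of OT time, special equipment or a senior opinion are not counted.

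The plan mentions no clustering by day, list or clinic, and no ICC, design effect, robust variance or random effect. It plans no confidence intervals.

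**The concern.** A chi-square on individual patients is valid if their outcomes are independent. Here patients share a list, and possibly the staff who judge whether to defer. They may also share the clinic where they were counselled; the plan says of the leaflet that "This leaflet will be handed over by the attending doctor in the Head neck OPD". Any of these could make outcomes on one day more alike than outcomes on different days.

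The direction matters. A doctor may work in both periods, so correlation by doctor could raise or lower the variance of the before/after contrast. An operating day cannot fall in both periods. Positive same-day correlation can therefore only raise that variance, and the chi-square does not see the increase. At stake is the 5% error rate of the significance rule for the primary end point.

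**Working it through.** **Inputs from the documents.** Two-sided alpha 0.05 ("The significance level of the test is 0.0500"); control proportion 0.20 ("The proportion in group 2 (the control group) is 0.2000"); 0.10 with the leaflet; 199 per group; 20 working days per month, so 2 x 20 = 40 operating days per period.

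**Assumption.** ICC of 0.01, 0.02 or 0.05; the documents give none.

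**1. The plan's own figure.** With pooled proportion 0.15:

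Power = Phi{[0.10 x sqrt(199) - 1.96 x sqrt(2 x 0.15 x 0.85)] / sqrt(0.20 x 0.80 + 0.10 x 0.90)} = Phi{(1.4107 - 0.9897) / 0.5} = Phi(0.842) = 0.80007.

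The stated 80.007% is reproduced, under independence of patients.

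**2. Patients per day.**
- 199 / 40 = about 5 analysed per day.
- The inflated total of 480 is 240 per period, and 240 / 40 = 6 per day.
- 12 per day x 40 = 480 per period if every head and neck case under general anaesthesia were eligible and took part. The throughput figure of 12-15 is therefore a ceiling.

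**3. Formulas.** With m patients per day:
- Design effect DE = 1 + (m - 1) x ICC
- True type I error of the chi-square = 2 x [1 - Phi(1.96 / sqrt(DE))]
- Power of a day-adjusted test: replace n by n / DE in step 1

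Example, m = 5, ICC 0.05: DE = 1 + 4 x 0.05 = 1.20. Then 1.96 / sqrt(1.20) = 1.79, giving a type I error of 7.4%. Adjusted power = Phi{[0.10 x sqrt(199 / 1.20) - 0.9897] / 0.5} = Phi(0.596) = 72%.

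| Patients/day (n per period) | ICC | DE | Chi-square type I error | Day-adjusted power |
|---|---|---|---|---|
| 5 (199) | 0.01 | 1.04 | 5.5% | 78% |
| 5 (199) | 0.02 | 1.08 | 5.9% | 77% |
| 5 (199) | 0.05 | 1.20 | 7.4% | 72% |
| 6 (240) | 0.01 | 1.05 | 5.6% | 85% |
| 6 (240) | 0.02 | 1.10 | 6.2% | 84% |
| 6 (240) | 0.05 | 1.25 | 8.0% | 79% |
| 12 (480) | 0.01 | 1.11 | 6.3% | 99% |
| 12 (480) | 0.02 | 1.22 | 7.6% | 98% |
| 12 (480) | 0.05 | 1.55 | 11.5% | 94% |

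**4. Simulation check.** A beta-binomial simulation (20,000 runs per scenario, 40 days per period, 20% in both periods) gave chi-square type I error of 5.8%, 5.9% and 7.5% at 5 per day for the three ICCs, and 5.2% at ICC 0. At 12 per day, separate runs gave 6.2-6.5%, 7.5-7.7% and 11.6-12.1%. A day-level t-test held about 5% throughout. At ICC 0 and about 200 per period its power was 80%, against 81% for the chi-square.

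**5. Effect on a result at the planned size.** For 40/199 against 20/199, the pooled z is 2.80 and P = 0.005. Dividing z by sqrt(1.20) gives P = 0.011 (5 per day, ICC 0.05). Dividing by sqrt(1.625) gives P = 0.028 (13.5 per day, ICC 0.05).

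**The case against.** The strongest reply is that the documents do not show any same-day correlation. The counted reasons are failures of the individual patient (fasting, investigations, medications), and the most obvious shared cause, lack of OT time, is excluded. The mechanisms that might produce correlation are inferences. The plan does not say that one team judges all deferrals on a day, or that patients on one list come from the same clinic. A late-running list could even give later patients more time to complete their fast. All of this stands. It makes the concern conditional, but the plan neither states nor checks the independence it relies on.

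Second, 12-15 is a throughput figure before eligibility. A reader might infer that this is the number analysed per day; the planned sample implies 5 or 6. Since all eligible patients are enrolled, larger numbers are possible, but 12 or more is a ceiling.

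Third, a result at the planned effect stays below 0.05 after adjustment (step 5 of the working). That is correct; the error rate matters for results nearer the threshold.

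Fourth, a reader might infer that a run of bad days in one period is the danger and that clustering by day would cure it. It would not: day-clustered methods treat different days as independent, so correlation across days is untouched, as is the confounding of leaflet with period.

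**Conclusion.** The point holds in conditional form. The documents establish that days are nested in periods, that several patients per day are enrolled, and that the chi-square has no allowance for clustering. If the same-day ICC is positive, the P-value is too small. Over an assumed ICC of 0.01 to 0.05, the type I error is about 5.5% to 7.4% at the planned sample and about 6.3% to 12% at the throughput ceiling. At the planned sample the adjusted power falls from 80% to between 78% and 72%. At the ceiling power stays at about 94% or more, so the issue there is the error rate.

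Two stronger readings are not supported. One is that the false-positive rate certainly exceeds 5%: with an ICC of zero there is no inflation from clustering. The other is that the plan reports intervals that are too narrow: it plans none, so this applies only to an unadjusted interval that a report might add. The change is worth making because it is cheap and the ICC is unknown.

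**What to change.** - Record for every patient the minor OT date, meaning the day on which the patient was called, so that a deferred patient stays with the list on which the deferral occurred.
- Add an analysis sentence: the before/after risk difference in postponement will be reported with a 95% CI and P-value from standard errors clustered by operating day. Either GEE with day as the cluster (available in SPSS, the software the plan names) or a t-test on daily proportions weighted by list size will do; choose one in advance. About 40 days per period is enough for robust errors.
- Report the plain chi-square alongside.
- State beside the 80.007% that it assumes independent patients, and give the power over an ICC range.

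The cost is one date field, one sentence and about one point of power if the ICC is zero. If correlation exists, the interval widens and power at about 200 per period falls as tabulated. The date should be captured as patients are enrolled, since it may not be recoverable later. The limits of a single before/after contrast remain and should be stated separately.
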